12.1 General considerations

All efficacy and safety endpoints will be summarized and analyzed using the full analysis set.

Estimated mean treatment differences (or ratios) will be presented together with two-sided 95% confidence interval (CI) for all endpoints analyzed. Data collected before randomization will only be summarized descriptively.

Recognizing that there may be more adjustment by the 670G software in the first two weeks of treatment in each crossover period, analyzation of data will be focused on week 3-7 of each cross over period.

12.2 Sample size calculation

The primary objective of the trial is to compare glycemic control with Fiasp® versus NovoLog® when used in the MiniMed 670G System in Auto Mode. The primary objective will be addressed by estimating the treatment difference (including 95% confidence intervals (CI)) for HbA1c and the PPG increment at 1 hour (meal test) after 6 weeks of treatment.

The trial population is assumed to be similar to that of a prior study with Fiasp® (reference 8) (exploratory, double-blind, randomized, 3×14-days, cross-over, single-center, active controlled trial evaluating external continuous subcutaneous infusion of insulin aspart in three different formulations in adult subjects with type 1 diabetes). In that trial, the within-subject standard deviation (SD) for 1-hour PPG increment (meal test) across all periods was 5.81, while the estimated treatment difference between Fiasp® and NovoLog® was -1.81 mmol/L (95% CI: -2.96 to -0.67).

Assuming that the treatment difference will be no less than that seen **in that study**, there is at least 80% power to detect a treatment difference with 36 subjects. Accounting for 10% dropouts, a total of 40 subjects should be randomized.

The subject population is furthermore in keeping with the treatment difference seen in the Onset 5 study (Reference 10), which was (ETD -0.91 mmol/L [95% CI -1.43; -0.39]; P = 0.001)

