5.7 Rationale for trial population

40 patients, accounting for 10% dropout rate, to achieve 80% power to detect 32 mg/dl treatment difference

6 Methods and Assessments

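### Section 12.2's within-subject SD of 5.81 gives about 25% power, not 80%; the figure is probably a variance, and the Onset 5 result does not support the assumed difference

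*Combined protocol and SAP*

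**What the plan says.** Section 12.2 plans on a cited three-period crossover trial. It reports that "the within-subject standard deviation (SD) for 1-hour PPG increment (meal test) across all periods was 5.81", with no unit, and in the same sentence that "the estimated treatment difference between Fiasp® and NovoLog® was -1.81 mmol/L (95% CI: -2.96 to -0.67"). The claim that follows is: "there is at least 80% power to detect a treatment difference with 36 subjects". It is made conditional on the size of the effect, in these words: "Assuming that the treatment difference will be no less than that seen" (the comparison is with the cited trial). For dropouts the section adds: "Accounting for 10% dropouts, a total of 40 subjects should be randomized".

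The section closes with a second reference: "The subject population is furthermore in keeping with the treatment difference seen in the Onset 5 study", and gives that difference as -0.91 mmol/L (95% CI -1.43 to -0.39). It does not say which endpoint this is.

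Section 5.7 repeats the result in other units, with 40 patients "to achieve 80% power to detect 32 mg/dl treatment difference", and gives no SD.

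**The concern.** An SD of 5.81 is more than three times the difference to be detected (5.81/1.81 = 3.2). With 36 subjects, even in a crossover, that ratio does not give 80% power. Either the SD label or the power claim is therefore wrong. Section 12.2 is the only calculation behind 36 evaluable and 40 randomized subjects, so the error goes to the sole justification of the sample size.

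The closing reference raises a second problem. The plan assumes a difference at least as large as 1.81 mmol/L and then cites, as consistent with it, an estimate half that size. A reader would take this as independent support for the planning value, which it is not.

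**Working it through.** **Inputs.** From section 12.2: variability 5.81; difference 1.81 mmol/L, 95% CI -2.96 to -0.67; 36 evaluable subjects; 10% dropout; Onset 5 difference 0.91 mmol/L, 95% CI -1.43 to -0.39. Section 12.2 states no test level. Two-sided 5% is assumed here from section 12.1: "Estimated mean treatment differences (or ratios) will be presented together with two-sided 95% confidence interval (CI) for all endpoints analyzed". The model in section 12.3 (treatment, period, random subject, only subjects with both meal tests) reduces to a paired contrast.

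**Parts that reproduce.** 36/0.9 = 40 randomized. 32 mg/dL divided by 18.016 is 1.78 mmol/L, so section 5.7 agrees with 1.81 mmol/L to within rounding.

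**Power.** SD of the paired difference = √2 × within-subject SD; SE = SD of difference/√36; noncentrality = difference/SE; noncentral t with 34 degrees of freedom.

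| Reading of 5.81 | SD of difference | SE | Noncentrality at 1.81 | Power at 1.81 | Power at 0.91 |
|---|---|---|---|---|---|
| Within-subject SD (as written) | 8.22 | 1.369 | 1.32 | 25% | 10% |
| SD of the paired difference | 5.81 | 0.968 | 1.87 | 44% | 15% |
| Within-subject variance (SD √5.81 = 2.41) | 3.41 | 0.568 | 3.19 | 87% | 34% |

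The largest within-subject SD that gives 80% power at 1.81 with 36 subjects is 2.66 mmol/L. As written, 80% power would need 164 evaluable subjects. Counting all 40 subjects gives 27%. A one-sided 5% test with 36 subjects gives 36% (37% by the normal approximation).

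**Check against the quoted CI.** Half-width (2.96 - 0.67)/2 = 1.145; SE = 1.145/1.96 = 0.584. In a complete crossover, SE = SD × √(2/N), so N = 2 × (SD/SE)².

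- If 5.81 is an SD: N = 2 × (5.81/0.584)², about 198 (200 to 201 with t quantiles).
- If 5.81 is a variance: N = 2 × 5.81/0.584², about 34 (36 to 37 with t quantiles).
- If 5.81 is in mg/dL (0.32 mmol/L): N is at most 3, so this reading is ruled out.

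Section 12.2 describes the cited trial as exploratory and single-center, which fits a size in the thirties far better than one near 200.

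**Using the CI alone.** The cited trial's N is not in the documents, so it is an assumption here. Implied SD = 0.584 × √(N/2):

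| Assumed N | Implied within-subject SD (mmol/L) | Power at 1.81, n = 36 |
|---|---|---|
| 20 | 1.85 | 98% |
| 34 | 2.41 | 87% |
| 60 | 3.20 | 65% |
| 100 | 4.13 | 44% |

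The 80% claim holds up to an N of about 41.

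**Onset 5.** 0.91/1.81 = 0.50, and the Onset 5 interval does not contain -1.81. The two estimates differ by 0.90. The Onset 5 SE is 0.52/1.96 = 0.265, so the SE of the difference between trials is √(0.584² + 0.265²) = 0.64, z = 1.40, p = 0.16. The trials are not shown to conflict, but Onset 5 gives no support for a minimum of 1.81.

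**Expected precision at n = 36.** Half-width = 2.03 × SE: 2.03 × 0.568 = 1.15 mmol/L (variance) or 2.03 × 1.369 = 2.78 mmol/L (SD).

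**The case against.** The best reply is that this is a labelling slip. The 25% reading needs about 200 completers in an exploratory single-center trial, so the two readings are not equally likely, and on the likelier one the power claim is true. This largely stands. It is why no change in enrolment is proposed, but it does not remove the contradiction in the printed text, which only the source can resolve.

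The variance reading is itself an inference from the CI, and the 87% depends on it. It also applies only to the 1-hour increment defined in section 12.3. The primary endpoint listed in section 4 is the 1-hour glucose level, for which section 12.2 gives no SD. Both limits are accepted.

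On Onset 5, the power statement is complete before that trial is mentioned, -0.91 enters no calculation, and its endpoint is not stated. This stands in part: the 34% applies only if the true difference on the planned endpoint is 0.91. It remains so that an estimate half the planning value does not support that value.

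The missing expected CI width is not an error. Section 12.2 addresses the objective by estimation, so the width would be useful, but it is an optional addition.

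**Conclusion.** The concern holds. The printed SD and the printed power in section 12.2 are incompatible: about 25% as written (44% if 5.81 is the SD of the paired difference) against a claim of at least 80%. The CI in the same sentence makes a variance of 5.81 (mmol/L)² the likelier meaning, with power of about 87% and an adequate sample size, but the documents do not prove it. The Onset 5 reference does not support the assumed minimum difference; at 0.91 mmol/L power is about 34% even on the favorable reading. These results assume a two-sided 5% test, 36 subjects with both meal tests, and a complete crossover in the cited trial. The inconsistency is certain; which reading of 5.81 is correct is not. It should be fixed, but it does not put the trial's conduct in question.

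**What to change.** 1. Check 5.81 against the cited source and state its unit and whether it is an SD or a variance. Giving that trial's N would let readers repeat the CI check.
2. If it is a variance, write in section 12.2: *within-subject variance 5.81 (mmol/L)², SD 2.41 mmol/L; 36 subjects give about 87% power at 1.81 mmol/L (two-sided 5%)*. If it is an SD, state that power at 1.81 mmol/L is about 25%.
3. Restate the power in section 5.7 to match.
4. First establish whether the Onset 5 figure is the same 1-hour increment. If so, replace the sentence with: *Onset 5 showed a smaller difference (-0.91 mmol/L, 95% CI -1.43 to -0.39); power at that difference with 36 subjects is about 34%* (10% if 5.81 is an SD). If not, say so and do not present it as support for 1.81.
5. Optionally, add the expected 95% CI half-width at n = 36: about 1.15 mmol/L at an SD of 2.41 mmol/L.

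The cost is a check of the cited sources and new wording in sections 12.2 and 5.7, with no change to enrolment or procedures.

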12.3 Primary endpoints

The primary endpoint is PPG increment at 1 hour (meal test) after 6 weeks of treatment (i.e. the difference in 1-hour PPG and PPG immediately prior to bolus administration). The primary endpoint will be used to address the primary objective of investigating postprandial glycemic control with Fiasp® compared to NovoLog® when used with the MiniMed 670G System in 'Auto Mode'.

The primary endpoint will be analyzed for subjects who perform the meal tests in both treatment periods, using the MiniMed 670G System in 'Auto Mode'. In other words, the treatment difference will be estimated in subjects who are able to manage 14 days of treatment with both Fiasp® and NovoLog® using the MiniMed 670G System in 'Auto Mode'.

The mean treatment difference stipulated by the estimand (including 95% CI), alongside treatment means, will be derived from a linear mixed model for repeated measurements. The model will include treatment, and period as factors, and subject as a random effect. Because the treatment difference is estimated in the population of subjects who are able to manage treatment with both Fiasp® and NovoLog®, i.e. subjects who contribute meal test data under both treatments, no special methods are needed to address missing data for the primary estimand.

12.4 Secondary endpoints

- Difference in HbA1c between periods will be assessed.
 - Glycemic excursion parameters. Time spent within glycemic ranges as below will be reported and analyzed. Time spent in specific ranges will be expressed as a percentage of total time on treatment.
 - o Time spent (%) within 70-180 mg/dl
 - o Time spent (%) < 70 mg/dl
 - o Time spent (%) >200 mg/dl
 - o Hypoglycemia
 - o Severe hypoglycemia

The time spent within 70-180 mg/dL, <70 mg/dL, and >200 mg/dL, and hypoglycemia is defined for each subject as the accumulated time in hours spent within the above intervals as recorded by the continuous glucose monitoring component of the MiniMed 670G system. Comparison between the NovoLog® and Fiasp® groups will be analyzed by using linear mixed modeling for repeated measurements for each range. The models will include treatment and period as factors, and subject as a random effect.

- Insulin related parameters
 - o Total daily dose
 - o change in %bolus and %basal from baseline
 - o Auto basal / basal amount (per day)
 - o Change in insulin : carbohydrate ratio from baseline
 - o Active insulin time

- Pump related parameters
 - o Time spent (%) in auto mode
 - o Time spent (%) in manual mode
 - o Auto mode exits (with reasons for exit)
 - o Infusion site reactions reported by patient
 - o Occlusion events reported by patient

Secondary endpoints will be assessed through duration of follow-up in the study.

13 Ethics

The trial will be conducted in compliance with ICH GCP and applicable regulatory requirements, and in accordance with the Declaration of Helsinki.

All Subjects included in the trial will be randomized to either Fiasp[®] or NovoLog[®].

The most common side effect of all available insulin preparations is hypoglycemia. The Investigator will explain to the Subject how they should check their BG meter and what precautions to take.

Subjects randomized in the trial will be transferred to a treatment regimen anticipated to be either better than or equal to the treatment they receive at the time they entered the trial.

At the end of treatment, the Subject and Investigator will decide on the best available treatment on the market.

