To compare Fiasp[®] in terms of glycemic control with a focus on post-prandial 1-hour plasma glucose level and system-based outcomes to NovoLog[®] insulin when used in the Medtronic mini Med 670G HCL system (operating in auto-mode) in patients with type 1 diabetes.

Secondary objectives

- Assessment of post-prandial glucose regulation (Continuous glucose monitor data, and 1,5 anhydroglucitol levels)
- Evaluation of cumulative glycemic control (HbA1c)
- Measurement of HCL parameters
- Reporting of Fructosamine levels

Endpoints

Primary Endpoint

- Post-prandial 1-hour plasma glucose levels at 6 weeks into start of therapy in each arm

Secondary Endpoints

- Post- prandial 2- hour plasma glucose levels at 6 weeks into start of therapy in each arm
- HbA1c and 1, 5 AG levels prior to cross-over, and at end of study
- Glycemic excursion parameters: Time spent within glycemic ranges as below will be reported and analyzed. Time spent in specific ranges will be expressed as a percentage of total time on treatment.
 - o Time spent (%) within 70-180 mg/dl
 - o Time spent (%) < 70 mg/dl
 - o Time spent (%) >200 mg/dl
 - o Hypoglycemia (differentiated as level 1 or level 2) (Reference 11)
 - o Severe hypoglycemia
- Insulin related parameters

- Total daily dose
- change in %bolus and %basal from baseline
- Auto basal / basal amount (per day)
- Change in insulin : carbohydrate ratio from baseline
- Active insulin time
- Pump related parameters
 - Time spent (%) in auto mode
 - Time spent (%) in manual mode
 - Auto mode exits (with reasons for exit)
 - Infusion site reactions reported by patient
 - Occlusion events reported by patient

This is an exploratory, single-center, randomized, open label, active-controlled, complete cross-over trial comparing safety and efficacy of Fiasp[®] versus NovoLog[®] when used in the Medtronic MiniMed 670G system in subjects with T1DM.

Study timeline:

FPV expected to be April 2019 with LPV in January 2020. The total duration of the trial participation for subjects is approximately 20 weeks as shown below:

Visit 1: Screening

Visit 2: Randomization /Treatment Period 1 Start / Day 0

Visit 3: Phone visit / 1 day after randomization

Visit 4: Phone visit / 1 week after randomization

Visit 5: Office visit / Week 2

Visit 6: Phone visit / Week 4

Visit 7: Office visit / Week 6 / Meal test

Visit 8: Office visit / Week 7/ Treatment Period 2 Start

Visit 9: Phone follow-up / 1 day after Visit 8

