Visit 10: Phone follow-up / 1 week after Visit 8

Visit 11: Office visit / Week 9

Visit 12: Phone follow-up / Week 11

Visit 13: Office visit / Week 13 / Meal test

Visit 14: Office visit Week 14

Visit 15: 30-day follow-up after EOT (phone)

The screening visit assesses subjects' eligibility. Eligible subjects will enter a two-week screening period. The screening period will provide subjects with an opportunity to become more familiar with the HCL, and will give the investigator opportunities to focus on pump use review, and review and training in study procedures as needed.

After the screening period, the subjects will be randomized (visit 2) to NovoLog[®] or Fiasp[®]. After 7 weeks on the initially assigned regimen, a cross-over will occur at Visit 8.

Rationale for study design

The screening period has been included to optimize HCL use, and assure adequate training of subjects in study procedures.

The 7-week randomized treatment period is needed to collect valid and adequate data to analyze safety and efficacy. A cross-over design will provide adequate control data.

The 6-week post-prandial readings and 1,5-AG levels will provide data on post-prandial glycemic control, and time-in-range and HbA1c measurements will provide data on cumulative glycemic control.

Fructosamine levels indicate the average level of blood glucose control over the past 2-3 weeks. These levels may be a more accurate measure of average blood glucose control after a 6 weeks treatment period than A1c which measures average glucose control over 2-3 months.

Safety will be assessed via hypoglycemia records, patient logs, and HCL parameters.

Treatment principles

During the screening period, the main focus will be ensuring all subjects are familiar with the HCL system, trouble-shooting potential problems, and reviewing study procedures. If the Investigator feels the subject should extend the screening period to further ensure familiarity with the HCL system, this will be allowed once.

In the treatment period, the investigators will strive to achieve glycemic targets of fasting and pre-prandial levels of 70-110 mg/dL in a treat-to-target fashion. All subjects must perform glucose calibration measurements as dictated by the 670G system CGM requirements.

At end of the treatment period, subjects will be switched to suitable approved regimen at the discretion of the investigator.

5 Study population

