6.1.8 Crossover (Visit 8)

At Visit 8 cross over the subject's will be dispensed study medication and switched to the comparative trial product. The Subject's will be instructed to change their pumps to manual mode for 1 week after the start of the crossover period. After 7 days of manual mode then subject will turn on auto mode for the duration of the treatment period.

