6.4.4 Fructosamine

Fructosamine levels indicate the average level of blood glucose control over the past 2-3 weeks. Please see section [2](#).

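### The Visit 13 HbA1c still reflects the other trial insulin, so its crossover contrast shrinks towards zero; fructosamine, which avoids this, has no planned comparison

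*Combined protocol and SAP*

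**What the plan says.** - **HbA1c analysis.** Section 12.4 states "Difference in HbA1c between periods will be assessed" and names no model for it. Section 12.2 says the primary objective will be addressed by estimating a treatment difference with 95% CI "for HbA1c and the PPG increment at 1 hour (meal test) after 6 weeks of treatment".
- **HbA1c sampling.** The secondary endpoints in section 4 list "HbA1c and 1, 5 AG levels prior to cross-over, and at end of study". The flow chart (section 2) places the draws at Visit 1, Visit 7 (six weeks after Visit 2) and Visit 13 (six weeks after Visit 8).
- **The switch.** At Visit 8, seven weeks after randomization, subjects are "switched to the comparative trial product" (section 6.1.8). There is no washout; the pump runs in manual mode for one week.
- **Memory of the two markers.** Section 6.4.4 states "Fructosamine levels indicate the average level of blood glucose control over the past 2-3 weeks". On fructosamine, the design rationale in section 4 adds "These levels may be a more accurate measure of average blood glucose control after a 6 weeks treatment period"; the comparison there is with HbA1c, whose memory it puts at two to three months.
- **Role of fructosamine.** It is drawn at Visits 2, 7 and 13. It appears among the secondary objectives as "Reporting of Fructosamine levels", but not in the endpoint lists of section 4 or anywhere in section 12.

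**The concern.** A marker that averages two to three months of glycaemia cannot forget, six weeks after a direct switch, the treatment that preceded the switch. At Visit 13 each sequence carries some effect of the insulin it has just left. That residue acts against the current treatment's effect, so it pulls the period 2 contrast, and with it the crossover estimate, towards no difference.

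Visit 7 does not have this problem. The insulin used before the trial also dilutes the Visit 7 value, but it is balanced across sequences by randomization and is part of any six-week HbA1c.

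A small or null HbA1c result could then be read as similar cumulative control when the design itself had shrunk the difference. Section 4 recognises that HbA1c is slow relative to a six-week period, but the analysis section does not act on it. The laboratory marker with a short enough memory is collected and not compared.

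**Working it through.** The plan gives no expected HbA1c difference, SD or sample size, so there is no HbA1c figure to reproduce. The check is how much of a true difference the planned contrast retains.

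**Inputs from the documents.** Visit 8 is 7 weeks after Visit 2. Visits 7 and 13 are each 6 weeks into their period. HbA1c memory is 2 to 3 months, taken as W = 8.7 or 13 weeks. Fructosamine memory is 2 to 3 weeks. Allocation to treatment order is 1:1.

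**Assumption.** The documents do not say how past weeks are weighted. Two shapes are used, with F(x) the total weight on the most recent x weeks, capped at 1:
- flat: F(x) = x/W
- linearly declining into the past: F(x) = 1 − (1 − x/W)²

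**Overlap.** Looking back from Visit 13, the weeks on the other trial insulin number 8.7 − 6 = 2.7 to 13 − 6 = 7.

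**Formulas, per unit of true difference.**
- Visit 7 contrast (the six-week difference): c = F(6)
- Weight of the other trial insulin at Visit 13: p = F(13) − F(6)
- Visit 13 contrast: c − p
- Balanced crossover estimate: [c + (c − p)]/2 = c − p/2
- Share of the six-week difference kept: 1 − p/(2c)

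| Weights | W (weeks) | c | p | c − p/2 | Share kept |
|---|---|---|---|---|---|
| Flat | 8.7 | 0.690 | 0.310 | 0.534 | 0.775 |
| Flat | 13 | 0.462 | 0.538 | 0.192 | 0.417 |
| Declining | 8.7 | 0.904 | 0.096 | 0.856 | 0.947 |
| Declining | 13 | 0.710 | 0.290 | 0.565 | 0.796 |

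Example, flat with W = 13: 1 − 0.538/(2 × 0.462) = 0.417. A simulated balanced crossover with 36 subjects, fitted with treatment, period and subject terms, returned the same c − p/2 values.

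The Visit 13 contrast alone, (c − p)/c, is 0.55 and −0.17 of the six-week difference (flat) or 0.89 and 0.59 (declining), for W = 8.7 and 13.

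**Delayed effect.** If no difference exists in the first L weeks of each period, then c = F(6 − L) and p = F(13 − L) − F(6). L = 1 stands for the manual-mode week and L = 2 for the two-week adjustment in section 12.1.

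| L (weeks) | Flat, W = 8.7 / 13 | Declining, W = 8.7 / 13 |
|---|---|---|
| 1 | 0.730 / 0.400 | 0.941 / 0.771 |
| 2 | 0.663 / 0.375 | 0.932 / 0.744 |

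**Visit windows.** With Visits 7 and 13 both at the +3 day limit and no delay, the share kept is 0.823 / 0.489 (flat) or 0.963 / 0.828 (declining).

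**Fructosamine.** With W = 2 or 3 weeks, F(6) = 1 and p = 0, so the share kept is 1.0. Even after a two-week delay, 6 − 2 = 4 weeks remain, which is longer than its memory.

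**The case against.** The strongest reply is that the size is unknown and may be small. Every retention figure rests on assumed weights; with declining weights and no delay the loss is only about 5% to 20%. No HbA1c difference or SD is given, so the bias cannot be put in HbA1c units or set against the width of the CI. It also arises only if a true difference exists. All of this stands, and it is why only the direction is claimed as firm.

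Second, the plan covers much of the ground. Section 4 acknowledges the slowness of HbA1c, the trial is labelled exploratory, HbA1c is listed as secondary in sections 4 and 12.4, and CGM time in range has a mixed model. That limits the consequence. It does not remove the HbA1c contrast, which 12.2 places under the primary objective. Nor does the focus on weeks 3 to 7 in section 12.1 help, since earlier weeks cannot be taken out of an HbA1c value.

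Third, absence from 12.4 proves little, because 1,5-AG and the 2-hour glucose are also missing there. That is fair, but those two are listed endpoints in section 4. Fructosamine is not, so the general CI rule in 12.1 for analyzed endpoints does not clearly reach it.

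Fourth, running HbA1c through the mixed model leaves it attenuated. That is correct. The gain comes from comparing fructosamine and from stating the HbA1c limitation, not from repairing HbA1c.

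Finally, the six weeks in the 12.2 sentence may qualify only the glucose increment. The flow chart still puts the HbA1c draws at six weeks.

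**Conclusion.** The concern holds, as a minor point on a secondary endpoint. On the protocol's own timings and stated HbA1c memory, the crossover contrast understates any true six-week difference. The direction was the same under both weightings, both memory lengths, delays of up to two weeks, and late visits.

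The size depends on weights the documents do not give. With the effect running from the switch, the contrast keeps 42% to 77.5% (flat) or 80% to 95% (declining) of the six-week difference. With a two-week delay it keeps 38% to 66% or 74% to 93%. These shares are relative to the six-week difference seen at Visit 7, not to a steady-state difference, and should be read as illustrative.

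Fructosamine at the same visits has no carryover under the stated memory, yet the plan does not compare it. The primary endpoint and the sample size are unaffected.

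**What to change.** 1. Add fructosamine at Visits 7 and 13 to the secondary endpoints in section 4 and to section 12.4, analysed with the mixed model already given there (fixed treatment and period, random subject).
2. In 12.4, define the HbA1c comparison as a between-treatment difference adjusted for period, from the same model. Label it supportive, and state that the Visit 13 value carries over exposure from period 1 and that this biases the contrast towards zero.
3. Reconcile the sentence in 12.2 that puts HbA1c under the primary objective with section 4 and section 12.3, where it is not the primary endpoint.

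The cost is wording in three places and one further model run. No sample or visit is added, since fructosamine is already drawn at Visits 2, 7 and 13. The downside is less weight on a more familiar marker.

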Slower than physiologic insulin effect at mealtime limits the ability to control the postprandial excursions in patients on insulin pumps including HCL systems. It is expected that Fiasp[®] in the 670G HCL system would lead to better postprandial control with more rapid insulin onset of effect. More rapid offset of insulin action might lead to less post meal hypoglycemia. Using Fiasp[®] in the 670G HCL might lead to improved % of time in range with its more rapid effect with pulses of insulin in the basal algorithm and lower post prandial glucose.

Fiasp[®] has not been studied in the 670G HCL system to date and its potential for optimizing glycemic control in the 670G HCL system needs to be evaluated.

The purpose of this study is to compare the efficacy and safety of Fiasp[®] versus NovoLog[®] in the Minimed 670G HCL system in T1DM subjects.

Both CGM and a standardized meal test will be used to evaluate the effect of Fiasp[®] vs. NovoLog[®] on postprandial glucose excursions in subjects on “Auto Mode” (active use of the HCL feature of the 670G). Time in range will be based on data downloaded from Medtronic Carelink data management software. The meal test will compare the physiological effect on postprandial glucose of Fiasp[®] vs. NovoLog[®] at the end of each treatment period. The use of a weight-based insulin dose calculation for the meal test aims to minimize inter-subject variability in insulin sensitivity. This will allow us to study insulin effect in a more direct manner, and gain insight into postprandial physiology.

7 week treatment periods during each crossover period will allow time for adjustment of the settings (I:CR and active insulin time) at appropriate intervals such as might be done in a clinical practice and then allow for 2-3 weeks of stable dosing to determine time in range during stable dosing (recognizing that the only settings that can be adjusted are I:CR and active insulin time). The 3 weeks after the dose adjustment period of stable dosing will compare the “time in range” in the Fiasp[®] vs. NovoLog[®] group in the 670G Hybrid Closed Loop System. The measurement of time in range during the post dose adjustment period makes this a more clinical, real world study as it compares efficacy over a period of weeks.

4 Research Design

Our hypothesis is that post prandial glucoses will be lower and time in range will be greater during the Fiasp[®] treatment period.

Objectives

Primary objective

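### Time in range divides CGM-recorded time by total treatment time: read literally, every percentage is scaled by sensor coverage and takes in the manual-mode week

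*Combined protocol and SAP*

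**What the plan says.** **Denominator.** The endpoint list in Section 4 and Section 12.4 carry the same sentence: "Time spent in specific ranges will be expressed as a percentage of total time on treatment". It is the only denominator the documents give.

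**Numerator.** Section 12.4 then says that the time in each range "is defined for each subject as the accumulated time in hours spent within the above intervals", and that this is time "as recorded by the continuous glucose monitoring component of the MiniMed 670G system". Section 3 adds: "Time in range will be based on data downloaded from Medtronic Carelink data management software". That names the data source but not the denominator.

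**Window.** Four descriptions could apply:
- Sections 4 and 12.4: all time on treatment, in periods of 7 weeks.
- Section 12.1: a focus on weeks 3-7 of each period, because the pump software may adjust more in the first two weeks.
- Section 3: two to three weeks of stable dosing after settings have been adjusted, later put as three weeks.
- The last line of Section 12.4: "Secondary endpoints will be assessed through duration of follow-up in the study".

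**Mode.** The primary objective compares the insulins "when used in the Medtronic mini Med 670G HCL system (operating in auto-mode"). Sections 6.1.3 and 6.1.8 put every subject in manual mode for the first week of each period.

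**Model.** Section 12.4 specifies a linear mixed model for each range, with treatment and period as factors and subject as a random effect. It does not say whether the response is the percentage or the hours.

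**The concern.** Time with no sensor reading cannot enter the numerator but stays in the denominator. It is therefore counted as time outside every range at once: neither in range, nor low, nor high. A subject with sensor gaps appears to have less time in range and also less time below 70 mg/dL. The second error makes a safety-relevant measure look better than the record supports. Coverage is not a listed output, so a reader could not undo the scaling.

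The denominator also brings in a scheduled manual-mode week and the early weeks that Section 12.1 means to set aside. Time in range is one of the two parts of the hypothesis in Section 4, although it is a secondary endpoint of an exploratory trial. The trial is open label, so a denominator and window left unsettled can be chosen after results are known.

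**Working it through.** The plan states no time-in-range value, coverage or expected difference, so there is no figure of its own to reproduce.

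**Inputs from the documents.** Periods of 7 weeks = 49 days; manual mode in week 1 of each (Sections 6.1.3, 6.1.8); focus on weeks 3-7 (Section 12.1); CGM-recorded time over total treatment time (Section 12.4); visit windows of ±3 days at Visits 8 and 14 (Section 2).

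**Assumed, for illustration only.** CGM coverage 80-95%; 70% of recorded time in range; 3% below 70 mg/dL; a 5-point treatment difference. The nearest figure in the documents is the 80% Auto Mode use criterion (Sections 5.2 and 5.4), which is not a CGM-coverage rule.

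**Step 1: what the literal definition measures.** Let p = (hours in range)/(hours recorded) and c = (hours recorded)/(hours on treatment). The literal percentage is (hours in range)/(hours on treatment) = p × c.

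**Step 2: levels.**

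| Recorded-time value | Reported at c = 0.80 | Reported at c = 0.95 |
|---|---|---|
| 70% in range | 70 × 0.80 = 56.0% | 70 × 0.95 = 66.5% |
| 3% below 70 mg/dL | 3 × 0.80 = 2.4% | 3 × 0.95 = 2.85% |

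**Step 3: treatment difference, equal constant coverage.** The difference becomes c × (p1 − p2): 5 points is reported as 5 × 0.80 = 4.0 to 5 × 0.95 = 4.75. The standard error is multiplied by the same c, so the ratio of estimate to standard error does not change.

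**Step 4: unequal coverage, as a sensitivity check only.**
- Equal control at 70%, coverage 90% against 85%: 63.0 − 59.5 = 3.5 points where there is no difference.
- 73% against 70%, coverage 90% against 85%: 65.7 − 59.5 = +6.2 instead of +3.0.
- The same values with coverage 85% against 90%: 62.05 − 63.0 = −0.95.

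The direction depends wholly on which insulin has the better coverage.

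**Step 5: window.** The manual week is 7/49 = 14.3% of a period. Weeks 1-2 are 14/49 = 28.6%, and weeks 3-7 are 35/49 = 71.4%. If the manual-week effect is a fraction f of a 5-point Auto Mode effect, the full-period difference at complete coverage is 5 × (6 + f)/7. This gives 4.29 points at f = 0 and 5.0 at f = 1. The documents do not give f.

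**Step 6: hours or percentage (a smaller matter).** A period can last 46-52 days. At 70% in range and full coverage that is 46 × 24 × 0.70 = 772.8 h or 52 × 24 × 0.70 = 873.6 h with identical control. Hours as the response would add noise, not bias.

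**The case against.** The strongest reply is that nobody would compute it this way. CGM-recorded time and CareLink downloads both fit a percentage of recorded time, and Section 12.1, which governs the statistical section, already sets aside the first two weeks and with them the manual week. That reading is possible, and it may be what was intended. But no section states recorded time as the denominator, and the denominator that is stated, twice, is a different one. Section 12.1 describes a focus and not a restriction, so it does not override Section 12.4. It is fair to call this an unreconciled inconsistency and not a flat contradiction.

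Other parts of the reply stand:
- The literal figure is the percentage of *recorded* time multiplied by coverage. It is the true percentage multiplied by coverage only if glucose during sensor gaps resembles glucose outside them.
- A reader might infer that the definition manufactures a treatment effect or costs power. With equal constant coverage it does neither. Only coverage that differs by insulin could inflate, shrink or reverse the difference, and the documents give no reason to expect that.
- A reader might infer that the manual week must dilute the effect. The background section reports effects of the faster insulin in pumps without closed-loop control, so the manual-week effect need not be zero.
- The follow-up sentence in Section 12.4 cannot extend CGM data past Visit 14, because Section 6.3.2 ends uploads there.
- Each range endpoint is labelled as a percentage, so hours as the model response is the less likely reading.

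**Conclusion.** The point holds as a wrong stated denominator and an unsettled window for the secondary time-in-range endpoints. Followed as written, the plan understates every level in proportion to missing sensor time: by 3.5 to 14 points on a value of 70% if coverage is 80-95%, a range that is assumed. Coverage that varies between subjects or periods adds noise. The effect of including the manual week on the treatment difference is unknown. On the illustrative 5 points it is at most about 0.7 of a point if that week's effect lies between none and all of the Auto Mode effect.

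The documents do not support a claim that the treatment comparison is biased, or that the 80% Auto Mode criterion shows what coverage will be. The primary endpoint, a meal-test plasma glucose measure, and the sample size are unaffected. The text should be corrected before analysis because the change is small and the reported levels cannot be interpreted without it.

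**What to change.** In Sections 4 and 12.4, define each endpoint as

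100 × (CGM time in the range) / (time with a recorded sensor glucose value)

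within one prespecified window. Use weeks 3-7 of each period: it is the only sub-window that the plan gives in week numbers, and it excludes the manual-mode week. Counting Visit 2 (Day 0 in Section 4) or Visit 8 as day 0, this is days 14-48, ending earlier if Visit 8 or Visit 14 falls earlier. Then:
- make Section 12.1 binding for these endpoints and reconcile Section 3 with it;
- remove total treatment time as the denominator, and exempt these endpoints from the follow-up sentence in Section 12.4;
- name the percentage, not accumulated hours, as the mixed-model response;
- report CGM coverage by treatment and period;
- state, before the data are seen, whether readings outside Auto Mode count and what minimum coverage a subject-period needs.

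The cost is wording in Sections 3, 4, 12.1 and 12.4. No new data are needed, since the uploads are already planned. There are two downsides: weeks 1-2 leave the comparison, as Section 12.1 already leans towards, and the recorded-time percentage still assumes that sensor gaps resemble recorded time. Reporting coverage lets a reader judge how much rests on that assumption.
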